11. SAFETY DEFINITIONS, RECORDING, REPORTING, AND RESPONSIBILITIES

Throughout the course of the study, every effort must be made to remain alert to possible AEs. If an AE occurs, the first concern should be for the safety of the participant. If necessary, appropriate medical intervention should be provided.

At the signing of the ICF, each participant and/or his/her legally authorized representative and/or main caregiver must be given the names and telephone numbers of site staff for reporting SAEs, pregnancies, overdoses, and medical emergencies. Throughout the protocol, the Sponsor is named, but reporting may be done through a CRO.

11.1. Definitions

11.1.1. Adverse Event

An AE is any untoward medical occurrence in a patient or clinical investigation subject (participant) administered a pharmaceutical product and that does not necessarily have a causal relationship with this treatment. An AE can therefore be any unfavorable and unintended sign (including an abnormal assessment such as an abnormal laboratory value), symptom, or disease temporally associated with the use of a medicinal (investigational) product, whether or not related to the medicinal (investigational) product.

Determination of whether an abnormal assessment (e.g., laboratory value, vital sign, and ECG) result meets the definition of an AE will be made by the Investigator. Abnormal results are not considered AEs unless one or more of the following criteria are met:

- The result meets the criteria for an SAE.
- The result requires the participant to receive specific corrective therapy.
- The result is considered by the Investigator to be clinically significant.

11.1.2. Serious Adverse Event

An SAE is any untoward medical occurrence that at any dose:

- Results in death.
- In the view of the Investigator, places the participant at immediate risk of death (a life-threatening event); however, this does not include an event that, had it occurred in a more severe form, might have caused death.
- Requires inpatient hospitalization or prolongation of existing hospitalization.
- Results in persistent or significant disability/incapacity.

- Results in a congenital anomaly/birth defect.
- Is a medically important event.

A medically important event is an AE that, in the opinion of the Investigator, may jeopardize the participant or may require intervention to prevent one of the other outcomes listed in the definition above. (Examples of such medical events include allergic bronchospasm requiring intensive treatment in an emergency room or convulsions occurring at home that do not require an inpatient hospitalization.)

11.1.3. Prescheduled or Elective Procedures or Routinely Scheduled Treatments

A prescheduled or elective procedure or a routinely scheduled treatment will not be considered an SAE, even if the participant is hospitalized. The study site must document all of the following:

- The prescheduled or elective procedure or routinely scheduled treatment was scheduled (or was on a waiting list to be scheduled) prior to obtaining the participant's consent to be in the study.
- The condition requiring the prescheduled or elective procedure or routinely scheduled treatment was present before and did not worsen or progress, in the opinion of the Investigator, between the participant's consent to be in the study and the time of the procedure or treatment.
- The prescheduled or elective procedure or routinely scheduled treatment is the sole reason for the intervention or hospital admission.
 - If a participant is hospitalized due to local requirements for administration of the study treatment, the hospitalization should not be considered an SAE unless one of the requirements in Section 11.1.2 is met.

11.2. Safety Classifications

11.2.1. Investigator Assessment of Events

All events must be assessed to determine the following:

- If the event meets the criteria for an SAE as defined in Section 11.1.2
- The relationship of the event to study treatment as defined in Section 11.2.2
- The severity of the event as defined in Section 11.2.3

11.2.2. Relationship of Events to Study Treatment or LP/Sham Procedure

The following definitions should be considered when evaluating the relationship of AEs and SAEs to the study treatment or the LP/sham procedure. Relationship of events to study treatment and relationship of events to LP/sham procedure will be documented separately.

Relationship of Event to Study Treatment or LP/Sham Procedure				
Not related	An AE will be considered "not related" to the use of the investigational product or the LP/sham procedure if there is not a reasonable possibility that the event has been caused by the product under investigation or the LP/sham procedure. Factors pointing toward this assessment include but are not limited to the lack of reasonable temporal relationship between administration of the investigational product or the LP/sham procedure and the AE, the presence of a biologically implausible relationship between the product or the LP/sham procedure and the AE, or the presence of a more likely alternative explanation for the AE.			
Related	An AE will be considered "related" to the use of the investigational product or the LP/sham procedure if there is a reasonable possibility that the event may have been caused by the product under investigation or the LP/sham procedure (e.g., bleeding from the puncture site). Factors that point toward this assessment include but are not limited to a positive rechallenge, a reasonable temporal sequence between administration of the investigational product or the LP/sham procedure and the AE, a known response pattern of the suspected product or the LP/sham procedure, improvement following discontinuation or dose reduction, a biologically plausible relationship between the product or the LP/sham procedure and the AE, or a lack of an alternative explanation for the AE.			

11.2.3. Severity of Events

The following definitions should be considered when evaluating the severity of AEs and SAEs:

Severity of Event				
Mild	Symptoms barely noticeable to participant or does not make participant uncomfortable; does not influence performance or functioning; prescription drug not ordinarily needed for relief of symptoms but may be given because of personality of participant.			
Moderate	Symptoms of a sufficient severity to make participant uncomfortable; performance of daily activity is influenced; participant is able to continue in study; treatment for symptoms may be needed.			
Severe	Symptoms cause severe discomfort; symptoms cause incapacitation or significant impact on participant's daily life; severity may cause cessation of treatment with study treatment; treatment for symptoms may be given and/or participant hospitalized.			

11.2.4. Expectedness of Events

Expectedness of all AEs will be determined by the Sponsor according to the current Investigator's Brochure for nusinersen.

11.3. Monitoring and Recording Events

11.3.1. Adverse Events

Any AE experienced by the participant between the time of signing of the ICF and the last study visit/telephone contact is to be recorded on the CRF, regardless of the severity of the event or its relationship to study treatment. At each study visit, the Investigator will assess the participant for AEs and will record any new AEs or updates to previously reported AEs on the CRF.

AEs that are ongoing when the participant completes or discontinues the study will be followed by the Investigator until the event has resolved or become stable. AE outcome will be recorded on the CRF, as applicable.

11.3.2. Serious Adverse Events

Any SAE experienced by the participant between the time of the signing of the ICF and the last study visit/telephone contact is to be recorded on an SAE form, regardless of the severity of the event or its relationship to study treatment. SAEs must be reported to the Sponsor within 24 hours or according to national law, as described in Section 11.3.3. Follow-up information regarding an SAE also must be reported within 24 hours or according to national law.

Participants will be followed for all SAEs until the last study visit/telephone contact. Thereafter, the event should be reported to the Sponsor only if the Investigator considers the SAE to be related to study treatment.

Any SAE that is ongoing when the participant completes or discontinues the study will be followed by the Investigator until the event has resolved, stabilized, or returned to baseline status.

11.3.3. Immediate Reporting of Serious Adverse Events

In order to adhere to all applicable laws and regulations for reporting an SAE, the study site must formally notify the Sponsor within 24 hours of the site staff becoming aware of the SAE or according to national law. It is the Investigator's responsibility to ensure that the SAE reporting information and procedures are used and followed appropriately.

Reporting Information for SAEs

A report must be submitted to the Sponsor regardless of the following:

- Whether or not the participant has undergone study-related procedures
- Whether or not the participant has received study treatment
- The severity of the event
- The relationship of the event to study treatment

To report initial or follow-up information on an SAE, fax or email a completed SAE form; refer to the Study Reference Guide's Official Study Contact List for complete contact information.

11.3.3.1. Deaths

Death is an outcome of an event. The event that resulted in death should be recorded on the appropriate CRF. All causes of death must be reported as SAEs within 24 hours of the site becoming aware of the event or according to national law. The Investigator should make every effort to obtain and send death certificates and autopsy reports to the Sponsor. The term "death" should be reported as an SAE only if the cause of death is not known and cannot be determined.

11.3.4. Suspected Unexpected Serious Adverse Reactions

SUSARs are SAEs that are unexpected and judged by the Investigator or the Sponsor to be related to the study treatment administered.

The Sponsor will report SUSARs to the appropriate regulatory authorities and Investigators as required, according to local law.

For Part B, which is blinded, appropriate personnel at the Sponsor will unblind SUSARs for the purpose of regulatory reporting. The Sponsor will submit SUSARs (in blinded or unblinded fashion) to regulatory agencies according to local law. For Part B, the Sponsor will submit SUSARs to Investigators in a blinded fashion.

11.4. Procedures for Handling Special Situations

11.4.1. Pregnancy

Participants should not become pregnant or impregnate their partners for the duration of the study. If a female participant becomes pregnant, study treatment must be discontinued immediately.

The Investigator must report a pregnancy occurring in a female participant or in the partner of a male participant from the first dose of study treatment by faxing or emailing the appropriate form to the Sponsor within 24 hours of the site staff becoming aware of the pregnancy. Refer to the Study Reference Guide's Official Study Contact List for complete contact information. The

Investigator or site staff must report the outcome of the pregnancy to the Sponsor. A pregnancy is not considered an AE and should not be recorded on the AE CRF.

Congenital abnormalities and birth defects in the offspring of male or female participants should be reported as an SAE if conception occurred during the study treatment period or 120 days from their last dose of study treatment.

11.4.2. Overdose

An overdose is any dose of study treatment administered to a participant or taken by a participant that exceeds the dose assigned to the participant according to the protocol. Overdoses are not considered AEs and should not be recorded as an AE on the CRF; however, all overdoses must be recorded on an Overdose form and faxed or emailed to the Sponsor within 24 hours of the site becoming aware of the overdose. An overdose must be reported to the Sponsor even if the overdose does not result in an AE. If an overdose results in an AE, the AE must be recorded. If an overdose results in an SAE, both the SAE and Overdose forms must be completed and faxed or emailed to the Sponsor. All study treatment-related dosing information must be recorded on the dosing CRF.

11.4.3. Medical Emergency

In a medical emergency requiring immediate attention, site staff will apply appropriate medical intervention, according to current standard of care. The Investigator (or designee) should contact the study's Medical Director. Refer to the Study Reference Guide's Official Study Contact List for complete contact information.

11.4.3.1. Unblinding for Medical Emergency

Part B is the only part of the study that is blinded. In a medical emergency when knowledge of the participant's treatment assignment may influence the participant's clinical care, the Investigator may access the participant's treatment assignment by IRT. The Investigator must document the reasons for unblinding in the participant's source documents. The Investigator is strongly advised not to divulge the participant's treatment assignment to any individual who is not directly involved in managing the medical emergency or to personnel involved with the analysis and conduct of the study. The Investigator can contact the Sponsor to discuss such situations.

11.5. Contraception Requirements

All female participants of childbearing potential and all male participants of reproductive age must ensure that effective contraception is used for the duration of the study. In addition, participants should not donate sperm or eggs for the duration of the study.

For the purposes of this study, females of childbearing potential are defined as all females physiologically capable of becoming pregnant, **unless** they meet one of the following conditions:

Postmenopausal

- 52 continuous weeks of natural (spontaneous) amenorrhea without an alternative medical cause and a serum follicle-stimulating hormone level > 40 mIU/mL
- 6 weeks after surgical bilateral oophorectomy with or without hysterectomy
- Posthysterectomy

For the purposes of the study, effective contraception is defined as the use of one of the following:

For females:

- Female surgical sterilization (e.g., bilateral tubal ligation), where applicable, according to local guidelines.
- Established use of oral, intravaginal, or transdermal combined (estrogen and progestogen containing) hormonal methods of contraception associated with the inhibition of ovulation
- Established use of oral, injected, or implanted hormonal methods of contraception
- Placement of an intrauterine device or intrauterine hormone-releasing system
- Barrier methods of contraception, where applicable according to local guidelines
- Bilateral tubal occlusion
- Sex with a male who has undergone surgical sterilization (with the appropriate postvasectomy documentation of the absence of sperm in the ejaculate)

For males:

- Vasectomy with negative semen analysis at follow-up. If documentation is not available, the participant must use contraception.
- Condoms with spermicide, where applicable according to local guidelines
- Sex with a woman who uses the methods described for females if she is of childbearing potential

True abstinence, when this is consistent with the preferred and usual lifestyle of the participant, can be considered an acceptable method of contraception based on the evaluation of the Investigator who should also take into consideration the duration of the clinical study. Periodic abstinence (e.g., calendar, ovulation, symptothermal, postovulation methods) and withdrawal are not considered acceptable methods of contraception.

Pregnancy reporting is described in Section 11.4.1.

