PedsQL and ACEND ²⁴		X			X ¹¹				X	
Ventilator Use ²⁵	X	X			X			X	X	
AE Recording	X									X
SAE Recording	X									X
Concomitant Therapy and Procedures Recording	X								D.	X

; ACEND = Assessment of Caregiver Experience with Neuromuscular Disease;

AE = adverse event; CGIC = Clinical Global Impression of Change; CHOP-INTEND = Children's Hospital of Philadelphia Infant Test of Neuromuscular Disorders; CSF = cerebrospinal fluid; D = day; ECG = electrocardiogram; EOS = end of study; ET = early termination; HFMSE = Hammersmith Functional Motor Scale Expanded; HINE = Hammersmith Infant Neurological Examination; ICF = informed consent form; LP = lumbar puncture; PedsQL = Pediatric Quality of Life InventoryTM; RULM = Revised Upper Limb Module; SAE = serious adverse event; SMA = spinal muscular atrophy; SMN1 = survival motor neuron-1 gene; SMN2 = survival motor neuron-2 gene; WHO = World Health Organization

¹ If the Screening visit occurs within 7 days before Day 1, screening assessments can be used for Day 1 predose assessments. The Screening period may be extended for up to 10 days for individuals who cannot complete the Day 1 visit within 21 days of signing the ICF, as long as they continue to meet other eligibility criteria.

² Participants who do not meet the criteria for contraception use will have their last visit on Day 302. Participants who meet the criteria for contraception use (see Section 11.5) will have a Day 302 and a Day 361 visit. Male participants who meet the criteria may complete the Day 361 visit via a telephone interview. Female participants who meet the criteria will return to the site for the Day 361 visit. Day 361 will take place at least 120 days after the final dose. For participants who meet the criteria for contraception use and enroll into the long-term extension study (232SM302) at the Day 302 visit, that will be their final visit in Study 232SM203.

³ Day 1 should be 4 months \pm 14 days after the participant's most recent nusinersen maintenance dose of 12 mg.

- ⁴ A serum pregnancy test will be performed locally in female participants of childbearing potential in the event of a positive or equivocal urine pregnancy test result.

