5.2. Study Duration for Participants

The total study duration for each participant will be approximately up to 420 days, divided as follows:

- Part A: approximately 323 to 410 days
 - Screening: 21 days
 - Loading period: 64 days
 - Maintenance period: 205 days
 - Follow-up: 33 to 120 days
- Part B: approximately 323 to 420 days
 - Screening: 21 days
 - Loading period: 64 days
 - Maintenance period: 215 days
 - Follow-up: 23 to 120 days
- Part C: approximately 323 to 382 days
 - Screening: 21 days
 - Loading period: 1 day
 - Maintenance period: 240 days
 - Follow-up: 61 to 120 days

Protocol 232SM203, Version 7 Escalating Dose and Randomized, Controlled Study of Nusinersen in SMA

Participants will have the following numbers of visits during the study:

[figure not shown]
• Part A: 8 to 9 visits

• Part B: 9 to 10 visits

• Part C: 5 to 6 visits

Visits during Days 1, 15, and 29 of the loading periods of Parts A and B and Day 1 of the loading period of Part C should be performed \pm 1 day from the nominal visit day. Visits during Day 64 of the loading period of Parts A and B and the maintenance period of Parts A, B, and C should be performed \pm 7 days from the nominal visit day. Visit days are calculated with respect to Day 1 (the date of first dose).

The end-of-study date for a participant may be the last study visit, last follow-up telephone conversation, last protocol-specified assessment, or, if the participant has ongoing SAEs that are being followed, the date of SAE resolution.

The Sponsor may terminate this study at any time, after informing Investigators. The Sponsor (or designee) will notify Investigators when the study is to be placed on hold, completed, or terminated.

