8. DISCONTINUATION OF STUDY TREATMENT AND WITHDRAWAL OF PARTICIPANTS FROM THE STUDY

8.1. Discontinuation of Study Treatment

A participant *must* permanently discontinue study treatment for any of the following reasons:

- The participant becomes pregnant. Study treatment must be discontinued immediately. Report the pregnancy according to the instructions in Section 11.4.1.
- The participant or the participant's parent(s)/legal guardian(s) withdraws consent to continue study treatment.
- The participant experiences an AE that necessitates permanent discontinuation of study treatment.
- The participant is not tolerating a given dose.
- The participant experiences a medical emergency that necessitates permanent discontinuation of study treatment (or unblinding of the participant's treatment assignment in Part B).
- At the discretion of the Investigator for medical reasons.
- At the discretion of the Investigator or Sponsor for noncompliance.

The primary reason for discontinuation of study treatment must be recorded in the participant's CRF.

Participants in Part B who discontinue treatment may remain in the study to continue the protocol-required tests and assessments described in Table 5 (unless the reason for discontinuation is to initiate treatment with a disallowed concomitant therapy per Section 7.6.1.2). Participants should return to the clinic according to the original visit schedule per Table 2 until the Day 302 study visit but will follow a reduced Schedule of Activities at these visits

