8.3. Withdrawal of Participants From the Study

Participants must be withdrawn from the study for any one of the following reasons:

- The participant or the participant's parent(s)/legal guardian(s) withdraws consent for participation in the study.
- The participant enrolls into another interventional clinical study in which an investigational treatment or approved therapy for investigational use is administered or initiates treatment with a disallowed concomitant therapy as described in Section 7.6.1.2.
- The participant is unwilling or unable to comply with the protocol.

The primary reason for the participant's withdrawal from the study must be recorded in the participant's CRF.

Participants should undergo an ET visit unless withdrawal is due to death or withdrawal of consent.

Participants who withdraw from the study may not be replaced.

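### Contraception, the donation ban and pregnancy avoidance run only for study duration, so an early leaver's obligation can lapse inside the protocol's own 120-day post-dose window

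*Protocol*

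**What the plan says.** Section 11.5 requires that participants of reproductive potential "must ensure that effective contraception is used for the duration of the study", and limits the ban on sperm and egg donation in the same way. Section 11.4.1 adds: "Participants should not become pregnant or impregnate their partners for the duration of the study". Neither section gives a term counted from the last dose. The only such term in Section 11.4.1 concerns reporting: congenital abnormalities in offspring "should be reported as an SAE if conception occurred during the study treatment period or 120 days from their last dose of study treatment".

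The 120 days reach participants through the schedule. Footnote 2 of Tables 3 and 4 (Part C) gives those who meet the contraception criteria a Day 302 and a Day 361 visit, and states: "Day 361 will take place at least 120 days after the final dose". Footnote 2 of Table 1 does the same for Part A with Day 389. In these tables ET shares a column with Day 302.

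For leavers, Section 8.3 says: "Participants should undergo an ET visit unless withdrawal is due to death or withdrawal of consent". It names nothing after that visit. Section 5.2 says: "The end-of-study date for a participant may be the last study visit, last follow-up telephone conversation, last protocol-specified assessment", with continued follow-up of a serious adverse event as a further option. Follow-up off treatment is set out for one part only, in Section 8.1: "Participants in Part B who discontinue treatment may remain in the study".

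**The concern.** The protocol treats a conception up to 120 days after dosing as relevant, and the Version 3 amendment rationale relates that interval to about five half-lives in the target tissue. That rationale also shows how the protection was delivered, namely by lengthening the study for those who must use contraception. A duty tied to study duration is then only as long as the individual's participation. A participant who has recently been dosed and then withdraws could be told, correctly under Sections 11.5 and 8.3, that the duty has ended.

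What is at stake is a safety instruction for a small group. Part B enrols infants and children under 10 years, so the people concerned are mainly Part C participants of reproductive potential, with Part A (ages 2 to 15) at the margin. Power, type 1 error and the efficacy comparisons are not involved.

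**Working it through.** **Inputs.** Dosing days are from Section 5.1: Part A on Days 1, 15, 29, 149 and 269; Part C on Days 1, 121 and 241. Final contraception-related visits are from footnote 2 of Tables 1, 3 and 4: Day 389 (Part A) and Day 361 (Part C). Durations are from Section 5.2.

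**Step 1: the plan's own figure.** The final visit minus the last dose is 389 − 269 = 120 days in Part A and 361 − 241 = 120 days in Part C. The maximum durations agree: 21 + 64 + 205 + 120 = 410 days (Part A) and 21 + 1 + 240 + 120 = 382 days (Part C). A completer who attends the final visit has no shortfall.

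**Step 2: early leavers.** Let t be the study day of the ET visit and d the day of the last dose received. There are two readings:

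- If the 120-day visit survives ET, the shortfall is 0.
- If the study ends for that person at ET, the shortfall is 120 − (t − d).

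The ET days below are assumptions chosen to show the range. The protocol does not predict when people leave.

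| Part | Last dose (d) | ET day (t) | Shortfall if the study ends at ET |
|---|---|---|---|
| C | 1 | 2 | 120 − 1 = 119 days |
| C | 1 | 15 | 120 − 14 = 106 days |
| C | 1 | 61 | 120 − 60 = 60 days |
| C | 1 | 120 | 120 − 119 = 1 day |
| C | 121 | 128 | 120 − 7 = 113 days |
| A (illustrative) | 29 | 64 | 120 − 35 = 85 days |

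**Step 3: how many people.** Cohort 1 of Part C aims for no more than 12 adults, and Cohort 2 has up to about 20, so the adult ceiling is about 12 + 20 = 32, plus any adolescents in Cohort 1. Only those of reproductive potential who also leave early are exposed. The protocol gives no withdrawal rate, so no headcount can be derived.

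**Step 4: do the texts settle the reading?** Footnote 2 describes participants who have a Day 302 visit and then the later one. It contains no sentence on what follows an ET visit. Section 8.3 contains no sentence on the 120-day visit. Section 5.2 can be read either way, since it allows both the last visit attended and the last assessment the protocol specifies as the end date. The texts leave the question open.

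**The case against.** The strongest reply is that footnote 2 already supplies the term. It requires both visits of everyone who meets the contraception criteria and makes no exception for early termination. ET is merged only with Day 302, so the later column still applies, and Section 5.2 counts up to 120 days of follow-up as part of study duration. The Version 3 rationale shows that this was the aim. This is a fair reading, and under it the shortfall is 0. It does not settle the matter, because it concerns a visit while the contraception and donation duties themselves have no post-dose term. It also sits awkwardly with someone who has been withdrawn from the study, and a site handling a withdrawal would look to Section 8.3.

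Other points stand in part. Some leavers, such as those who withdraw consent or cannot be reached, would not attend another contact whatever the text said. Stopping treatment is not the same as leaving the study, and Section 8.1 does not say that Part A or C participants who stop dosing must leave. There is a pregnancy test at Day 302/ET, pregnancy reporting has no stated end, and birth-defect reporting already covers the 120 days. These safeguards help detection, but they do not extend the duty to avoid conception. Part A is probably finished: Section 5.1 places its loading period before Part B began, Version 7 is dated two years after Version 6, and Part A lasts at most about 410 days.

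A reader might go further and infer that the protocol contradicts itself, or that everyone is under-protected. The texts do not support either. The post-dose term is unstated rather than contradicted, and completers are fully covered. A reader might also infer a gap for Part C participants who "enroll into the long-term extension study (232SM302) at the Day 302 visit, that will be their final visit in Study 232SM203". That cannot be shown, because they pass to a study with its own requirements, which are not at hand.

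**Conclusion.** The point holds as a minor one. Sections 11.5 and 11.4.1 state a rule that gives the intended 120 days only if the participant stays until the final visit. For a participant of reproductive potential who leaves early, the protocol does not say that the duty or the 120-day visit continues. The shortfall lies between 0 days and 120 minus the time since the last dose; the upper figure assumes that the study ends for that person at ET. The group is small: within about 32 Part C adults plus any adolescents, it is those of reproductive potential who leave early. Part A is illustrative only. There is no effect on efficacy inference.

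**What to change.** In Sections 11.5 and 11.4.1, extend contraception, the donation ban and pregnancy avoidance to at least 120 days after the last dose received, and state that participants entering 232SM302 follow that study's requirements. In Section 8.3 and in footnote 2 of Tables 1, 3 and 4, state that participants who meet the contraception criteria and have an ET visit also have the existing 120-day contact, counted from the last dose received, unless consent is withdrawn. As now, this would be by telephone for males and a site visit with a pregnancy test for females.

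The cost is one clause in two sections, one sentence in Section 8.3 and the footnotes, and one extra contact of an existing type for a few early leavers. The schedule for completers does not change.
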